### 8.3. General Considerations

Summary statistics, listings, and statistical analyses will be performed for patients included in the relevant analysis sets.

For continuous data, summary statistics will include the arithmetic mean, arithmetic standard deviation, median, minimum, maximum, and number. For log-normal data (e.g., the PK parameters, the activity-time curve and elimination half-life of absorbed doses to CSF and

blood), the geometric mean and geometric coefficient of variation will be presented instead of mean and SD. For categorical data, frequency counts and percentages will be presented. Data listings will be provided for all patients up to the point of withdrawal, with any patients excluded from the relevant analysis set highlighted. For the calculation of summary statistics, listings, and statistical analysis, unrounded data will be used.

For the time to event efficacy endpoints, patients who do not have an event will be censored at the date of their last evaluation. If partial dates are present, a conservative approach will be used. If partial dates are present for efficacy time to event endpoints, missing months and/or days will be imputed as January and the first day of the month, respectively. AEs with a missing start date or time that leads to ambiguity in whether the AE is treatment-emergent will be considered treatment-emergent. It is unlikely that other missing of safety data will occur in the targeted patient population, but in case it happens the data will not be imputed.

When the last patient in Part 1 has completed the EOT visit, all available data for that part will be reported.

For Part 2, full efficacy and safety analyses will be performed when the last patient completes week 52 assessments, dies, or is lost to follow up. An updated long term survival analysis will be performed when the last patient has reached the 104 week visit, dies, or is lost to follow-up.

Data analysis will be performed using SAS® Version 9.3 or higher.

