### 2.2.2.2. *Part 2*

- PK profile of Lu-DTPA-omburtamab in blood and CSF.
- Response, as defined by the RAPNO criteria (as determined from MRI assessments, neurological examination, and CSF cytology).
  - ORR, calculated as the proportion of all evaluable patients achieving a response (PR or CR) as best overall response at end of Cycle 1 and Cycle 3, EOT Visit, and at each Follow-up Visit.
- Investigator-assessed DoR, defined as the time from first response (CR or PR) to progression.
- PFS, defined as the time from first treatment to date of leptomeningeal progression or death from any cause, whichever comes first.
- OS defined as the time from first treatment to date of death.

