### 7.3.2. Response Evaluation, Overall Response Rate, and Duration of Response

Response, as defined by the RAPNO criteria (Warren et al. 2018; see Appendix 6) will be assessed in Part 1 at the EOT Visit. In Part 2, response will be assessed at end of Cycle 1 and Cycle 3, EOT Visit, then 26, 39, and 52 weeks post first dose, followed by 78 and 104 weeks post first dose of Lu-DTPA-omburtamab. Notably, objective response and stable disease requires that all criteria are met, while progression is defined when any of the PD criteria are met.

The ORR will be calculated from baseline MRI scans and from scans after the dosing of Lu-DTPA-omburtamab using 2 methods: firstly, by considering MRI data, neurological examination, and CSF cytology data together (RAPNO criteria); secondly, by considering CSF cytology data only. ORR will be defined as the proportion of all evaluable patients achieving a CR or PR as best overall response at the time of assessment.

Investigator-assessed DoR (Part 2) is defined as the time from response (CR or PR) to progression. Patients without any sign of progression will be censored at the date of their last PFS assessment.

In Part 1 and Part 2, the baseline CSF cytology assessment must be completed within 3 weeks prior to the first Lu-DTPA-omburtamab treatment dose infusion. Cerebrospinal fluid cytology should be assessed as positive/negative. Cerebrospinal fluid cytology will be assessed in Part 1 at screening, the EOT Visit, and in Part 2 at screening, end of Cycle 1 and Cycle 3, EOT Visit, and at each Follow-up Visit.

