### **8.4.1. Part 2 Efficacy Analysis**

Overall survival at 1 and 2 years post first dose will also be estimated using Kaplan-Meier methods. Patients not deceased will be censored at the last date known to be alive. The median PFS time and the proportion of patients without PFS events at 1 and 2 years post first dose will be estimated using Kaplan-Meier methods, along with their 95% confidence intervals. Results will be displayed in Kaplan-Meier plots. The ORR according to RAPNO criteria (MRI, neurological examination, and CSF cytology), as well as according to CSF cytology alone, will be assessed. The 95% confidence intervals will be calculated using the Clopper-Pearson exact methodology. Investigator-assessed DoR will be estimated using Kaplan-Meier methods. The median DoR and corresponding 95% confidence interval will be calculated.

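### The January / day-1 rule for partial efficacy dates has no lower bound and treats start and end dates alike, so it can give impossible PFS or OS times and can lengthen DoR

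*Combined protocol and SAP*

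**What the plan says.** Section 8.3 (General Considerations) first states the intent: "If partial dates are present, a conservative approach will be used". For efficacy time-to-event endpoints it then gives the rule: "missing months and/or days will be imputed as January and the first day of the month, respectively". It sets no floor and no exception, and it does not distinguish a date that starts an interval from one that ends it.

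Section 2.2.2.2 defines the endpoints to which the rule applies. For PFS the text is: "PFS, defined as the time from first treatment to date of leptomeningeal progression or death from any cause, whichever comes first". The same origin holds for OS, which ends at death. DoR differs in having a start date of its own: "Investigator-assessed DoR, defined as the time from first response (CR or PR) to progression".

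The trial will hold dates on which a patient is known to be event-free. Section 7.3.2 fixes the Part 2 visits: "response will be assessed at end of Cycle 1 and Cycle 3, EOT Visit, then 26, 39, and 52 weeks post first dose". Two later visits come at weeks 78 and 104. Section 8.4.1 uses a known-alive date for censoring OS: "Patients not deceased will be censored at the last date known to be alive". Neither kind of date is used to bound an imputed event. Sections 7.3.1 to 7.3.3 and 8.4.1 cover definitions, censoring and Kaplan-Meier estimation, and they add no bound.

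**The concern.** PFS and OS run from first treatment. If the year of an event is known but the month is not, 1 January precedes first dose whenever the event falls in the calendar year of first dose (unless that dose was itself on 1 January). The result is a negative time, which Kaplan-Meier estimation cannot use, and the plan does not say what would be done with it. An imputed date can also fall after first dose but before a visit at which the patient was recorded as progression-free or alive, which contradicts the trial's own data.

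DoR has a different problem. The response date starts the interval, so moving it earlier makes the duration longer. That is the opposite of conservative.

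At stake are the PFS, OS and DoR estimates for about 24 Part 2 patients. Without a rule fixed beforehand, an ad hoc repair would be chosen after the data are seen.

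**Working it through.** The plan states no figure on this point, so there is none to reproduce.

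**Inputs.** The rule is from section 8.3 and the time origins from 2.2.2.2. Visit times are from 7.3.2 and Table 8 (Cycle 1 and Cycle 3 end-of-cycle visits at days 29 and 99, then weeks 26, 39, 52, 78 and 104). The recruitment window is Q4-2021 to Q3-2023 (Synopsis), and Part 2 has 24 patients (8.1). Three things are assumed: first doses are uniform over the calendar, event times in step 2 are exponential, and medians are 4, 6 and 12 months. The documents give no expected median and no rate of partial dates.

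**1. Worked dates.**
- First dose 15 Sep 2022, progression-free on 1 Dec 2022, true progression 20 Dec 2022 recorded only as 2022. True PFS is 96 days. The rule gives 1 Jan 2022, which is -257 days. A floor at the day after the last progression-free date (2 Dec) gives 78 days.
- First dose 5 Sep, death 25 Sep recorded only as September. True OS is 20 days. The rule gives 1 Sep, which is -4 days.

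**2. Share of partial event dates placed on or before first dose.** This needs the event in the same calendar year (or month) as first dose. With first dose uniform over the period and λ the event rate per period, the share is 1 - (1 - e^(-λ))/λ.

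| Assumed median | λ per year = 12 × 0.693/median | Year-only share | λ per month = 0.693/median | Day-missing share |
|---|---|---|---|---|
| 4 months | 2.079 | 1 - 0.875/2.079 = 58% | 0.173 | 8% |
| 6 months | 1.386 | 1 - 0.750/1.386 = 46% | 0.116 | 6% |
| 12 months | 0.693 | 1 - 0.500/0.693 = 28% | 0.058 | 3% |

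The backward shift averages 182 days with the month missing (maximum 364, or 365 in a leap year) and 15 days with only the day missing (maximum 30).

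**3. Events dated at scheduled visits.** Running through every first-dose date in the recruitment window, with the month missing, the imputed date precedes first dose in 92% of cases for an event at day 29. The share is 73% at day 99, 50% at week 26, 25% at week 39 and 0% from week 52. With only the day missing it is 5% at day 29 and 0% from day 99.

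**4. Imputed date before a known event-free visit, month missing.** This needs both visits in one calendar year. For a 13-week gap the share is 1 - 91/365 = 75%, and for a 26-week gap 1 - 182/365 = 50%. For a death uniform within the gap, enumeration gives 87% (weeks 26 to 39) and 75% (weeks 52 to 78). With only the day missing these become 15% and 8%.

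**5. DoR.** Response 13 Oct 2022, progression 13 Apr 2023: true DoR is 182 days.
- Response day missing: 1 Oct to 13 Apr = 194 days.
- Response month missing: 1 Jan 2022 to 13 Apr 2023 = 467 days.
- Both days missing: 1 Oct to 1 Apr = 182 days.
- Both months missing: 1 Jan 2022 to 1 Jan 2023 = 365 days.

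**6. Effect on a landmark estimate.** One event moved across 1 or 2 years changes the Part 2 estimate by 1/24 = 4.2 percentage points, ignoring censoring.

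**The case against.** The strongest reply is that partial dates will be rare and mostly mild. Response rests on dated MRI, cytology and neurological examinations at fixed visits. Fatal adverse events carry an end date. SAEs up to five weeks after the last dose are reported within 24 hours. Appendix 2 provides for edit checks, queries and source verification. Most gaps that remain would lack only the day, where the shares in step 2 are 3% to 8%. Those shares are too high for visit-dated progression, because the exponential model allows events before the first scheduled assessment; step 3 gives 5% at day 29 and 0% from day 99. For PFS and OS event dates, moving the date earlier is conservative, as intended. A negative time would be obvious among 24 patients.

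Most of this stands, and it limits the size of the point. It does not supply the missing floor. Two plausible routes to a partial date remain: deaths reported from off site, and progression backdated to the start of neurological decline under the footnote to Appendix 6. The general promise of a conservative approach cannot be taken as an implied floor, since the explicit rule has none and works the other way for a response date.

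A reader might infer more than the documents support:

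- **Censoring is also wrong.** Applying the rule to a partial last-alive date is not an error. Within a recorded month or year in which the patient was known alive, only the first day is certain to be event-free. Section 8.3 also does not clearly extend the rule to censoring dates.
- **Any half-year shift moves the curve by about 4 points.** A shift moves a step in time. The 1- or 2-year estimate changes by about 4 points only if the event crosses that landmark, and 1/24 is not the denominator for DoR, which uses responders only.
- **DoR is always inflated.** If the progression date is also partial, the shifts can cancel, as with both days missing in step 5.

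**Conclusion.** The point holds as a defect in a stated rule. Section 8.3, followed literally, can place progression or death before first dose or before a date on which the patient was known event-free. It also lengthens DoR when only the response date is partial, against its stated intent.

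The percentages describe dates that are already partial and rest on uniform first-dose dates and the assumed event times. They do not estimate how many Part 2 patients will be affected, and the documents do not support any claim that the PFS, OS or DoR results will be materially distorted. The severity is minor. The endpoints are secondary and descriptive, the trial has a single arm, and neither the primary endpoints nor the sample-size reasoning uses these times.

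**What to change.** Replace the single rule in section 8.3 with two.

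1. **Progression and death dates.** Impute the later of (a) the January / day-1 date and (b) the day after the last date known event-free, never before first dose and within the recorded month or year. The last event-free date is the last progression-free assessment for PFS and for the end of DoR, and the last date known alive for death. Where progression is backdated under the Appendix 6 footnote, use the last assessment before the recorded onset.
2. **Response dates (start of DoR).** Use the latest date consistent with the recorded partial date and the assessment visit.

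The cost is a sentence or two of SAP text and a bound in the derivation program. It should be settled before the week 52 analysis so that it is not chosen after the dates are seen.

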## **8.4. Efficacy Analysis**

The FAS will be used for all efficacy endpoints.

### **8.4.1. Part 2 Efficacy Analysis**

Overall survival at 1 and 2 years post first dose will also be estimated using Kaplan-Meier methods. Patients not deceased will be censored at the last date known to be alive. The median PFS time and the proportion of patients without PFS events at 1 and 2 years post first dose will be estimated using Kaplan-Meier methods, along with their 95% confidence intervals. Results will be displayed in Kaplan-Meier plots. The ORR according to RAPNO criteria (MRI, neurological examination, and CSF cytology), as well as according to CSF cytology alone, will be assessed. The 95% confidence intervals will be calculated using the Clopper-Pearson exact methodology. Investigator-assessed DoR will be estimated using Kaplan-Meier methods. The median DoR and corresponding 95% confidence interval will be calculated.

## **8.5. Safety Analysis**

### **8.5.1. Dose-Limiting Toxicities**

DLTs observed during the DLT evaluation period, i.e., within 5 weeks after the dosimetry dose in Cycle 1 of the dose escalation will be listed and summarized by Medical Dictionary for Regulatory Activities (MedDRA) system organ class (SOC) and preferred term (PT). DLTs observed outside the DLT evaluation period will be presented in a listing. The information from

the DLTs will be used to guide the escalation and ultimately determine the MTD. Furthermore, the information will be used to make recommendations regarding the RP2D. The evaluation of DLTs will be based on the DLT evaluable analysis set.

### **8.5.2. Adverse Events**

The Safety Analysis Set will be used for all safety analyses except for evaluations of DLTs. Adverse events will be coded using the Medical Dictionary for Regulatory Activities (MedDRA) Version 22.1 or later. Adverse events will be regarded as TEAEs if they occur after first administration of Lu-DTPA-omburtamab. Related AEs are defined as ADRs.

Listings will be made of all AEs. Non-TEAEs will be listed separately. All TEAEs, ADRs, AESIs, SAEs, and serious ADRs will be summarized by MedDRA SOC and preferred terms for each treatment group. The summaries will include number of AEs, number of patients, and percentage of patients reporting these AEs and will be tabulated by SOC and preferred term. TEAEs will also be summarized by severity and by relationship to IMP.

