In Part 2, all treatment cycles will consist of a treatment dose on Day 1; the dose level will be the RP2D determined in Part 1. Patients who are not discontinued from treatment will be eligible for up to 5 treatment cycles in Part 2. Dose reductions due to toxicity are permitted in Part 2 only.

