## 2. OBJECTIVES AND ENDPOINTS

### 2.1. Objectives

#### 2.1.1. Primary Objectives

The primary objective of Part 1 (dose-escalation phase) of this trial is to explore the tolerability of up to 2 cycles of intracerebroventricular Lu-DTPA-omburtamab treatment in pediatric and adolescent patients with recurrent or refractory medulloblastoma. The MTD and/or the RP2D for Part 2 will be determined.

The primary objective of Part 2 (cohort-expansion phase) of this trial is to establish a safety profile of repeated dosing of Lu-DTPA-omburtamab in pediatric and adolescent patients with recurrent or refractory medulloblastoma.

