### 2.2. Endpoints

#### 2.2.1. Primary Endpoints

The primary endpoint of Part 1 is number of DLTs.

The primary endpoint of Part 2 is number and severity of TEAEs.

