## 8. SAMPLE SIZE AND DATA ANALYSES

### 8.1. Determination of Sample Size

In Part 1, the chosen sample size is customary for studies of this nature and is not based on statistical considerations. It is estimated that up to 25 patients will participate in Part 1, based on 5 dose levels being recruited. Actual number of patients will depend on the number of DLTs observed.

For Part 2, a sample size of 24 patients provides at least 90% probability to detect an AE occurring in 10% of exposed patients.

The assumption is that 20 out of the 24 patients in Part 2 are evaluable. With 20 patients evaluable for response and a response rate of 25% (~ to 5 responders out of 20), the lower limit of the 95% confidence interval will be 9%.

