### 8.2. Analysis Populations

The following analysis sets will be included for this trial:

**Safety Analysis Set:** will consist of all patients who received at least 1 dose of trial treatment (treatment dose or dosimetry dose).

**DLT Evaluable Analysis Set:** will include patients in the dose escalation who as a minimum is evaluated during the 5 weeks DLT evaluation period, or who has a DLT during the DLT evaluation period. This analysis set is a subset of the Safety Analysis Set.

**Full Analysis Set (FAS):** will consist of all patients in the Safety Analysis Set.

**Dosimetry Analysis Set (Part 1 only):** will consist of all patients who received the dosimetry dose and have evaluable data for absorbed doses to CSF and blood or for whole-body planar scan.

**PK Analysis Set:** will consist of all patients who received at least 1 treatment dose of trial drug and have evaluable PK data.

Efficacy will be analyzed using the FAS. Safety will be analyzed using the Safety Analysis Set. Dosimetry and absorbed doses to CSF and blood will be analyzed using the Dosimetry Analysis Set. Pharmacokinetics will be analyzed using the PK Analysis Set.

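### Part 2 is about the safety of repeated dosing, but TEAEs are summarised only pooled over all cycles, so toxicity arising in later cycles is diluted if patients stop early and cannot be told apart from first-dose toxicity

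*Combined protocol and SAP*

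**What the plan says.** Section 2.1.1 says that the Part 2 primary objective "is to establish a safety profile of repeated dosing of" the study drug. Section 2.2.1 adds: "The primary endpoint of Part 2 is number and severity of TEAEs". Patients may receive up to five cycles (Section 3.1.3).

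Section 8.5.2 counts any AE after the first administration as a TEAE and uses the Safety Analysis Set for everything except DLTs. Section 8.2 defines that set as everyone given at least one dose. TEAEs are to be "summarized by MedDRA SOC and preferred terms for each treatment group", as numbers of events, numbers of patients and percentages of patients, and also by severity and by relationship. All AEs are listed. Neither Section 8 nor the synopsis plans a summary by cycle of onset, by number of cycles received or by cumulative activity.

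On size, Section 8.1 states that "a sample size of 24 patients provides at least 90% probability to detect an AE occurring in 10% of exposed patients". On dose, the synopsis says: "Dose reductions due to toxicity are permitted in Part 2 only".

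**The concern.** Part 2 has one planned dose level, so a summary per treatment group puts every cycle into one column. A patient who received one cycle stays in the denominator for a toxicity that can only arise after the fourth or fifth dose. A preferred term reported by three patients after their first dose and one reported by three patients in Cycle 5 give the same line in the table.

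The protocol itself treats accumulation as an open question. Section 3.1.2 allows the RP2D to be set below the MTD because of toxicity building up over two cycles. Section 3.2 keeps patients with two or more recurrences out of Part 2 because short survival could prevent a safety assessment over five cycles. Part 1 stops at two cycles, so Part 2 is this trial's only source of data on Cycles 3 to 5. The one planned Part 2 DMC meeting comes when the eighth patient has completed Cycle 1 dosing (Section 4.4), so the final tables carry most of the weight on later cycles.

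**Working it through.** **Inputs from the documents.** n = 24 patients in Part 2 and an AE rate of 10% (Section 8.1); up to five cycles (Section 3.1.3); all dosed patients as denominator (Sections 8.2 and 8.5.2).

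**Input not in the documents.** The number of patients who reach each cycle. Section 8.1 says "The assumption is that 20 out of the 24 patients in Part 2 are evaluable", but that concerns evaluability for response and is not a retention figure. The number is therefore an assumption and is shown as a range.

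**Step 1: the plan's own figure.** The chance of at least one case is 1 − (1 − p)^n. With p = 0.10 and n = 24, 1 − 0.9^24 = 92.0%, which agrees with Section 8.1. The smallest n that keeps 90% is 22 (90.2%); n = 21 gives 89.1%.

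**Step 2: dilution.** Let n_c be the number of patients dosed in a cycle and k the number who have a given toxicity in that cycle and at no other time. The rate among those dosed is k/n_c and the pooled table shows k/24, so the pooled figure is n_c/24 of the rate among those dosed.

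**Step 3: results for k = 3.** The last column uses the Step 1 formula with n = n_c and p = 0.10.

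| Dosed in the cycle (assumed) | Rate among those dosed | Shown in pooled table | Ratio n_c/24 | Chance of at least one case at a 10% rate |
|---|---|---|---|---|
| 24 | 12.5% | 12.5% | 1.00 | 92.0% |
| 20 | 15.0% | 12.5% | 0.83 | 87.8% |
| 16 | 18.8% | 12.5% | 0.67 | 81.5% |
| 12 | 25.0% | 12.5% | 0.50 | 71.8% |
| 8 | 37.5% | 12.5% | 0.33 | 57.0% |

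The third column never changes, which is the loss of information. The last column changes only because n_c changes; table layout does not enter the formula.

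**Step 4: is early stopping plausible?** Section 4.3.2.1 requires treatment to stop for progression and for several toxicities. Entry requires a life expectancy of at least 3 months (Section 4.1), while the Cycle 4 dose falls on Day 106 and the Cycle 5 dose on Day 141 (Appendix 3, Table 8, footnote 1), that is 105/7 = 15 and 140/7 = 20 weeks after the first dose. As an illustration only, a constant loss of 10% per cycle leaves 24 × 0.9² = 19.4 patients at Cycle 3 and 24 × 0.9⁴ = 15.7 at Cycle 5. A loss of 20% leaves 24 × 0.8² = 15.4 and 24 × 0.8⁴ = 9.8.

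**The case against.** Four arguments deserve weight.

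*The pooled incidence is a legitimate answer.* The regimen is up to five cycles, and the proportion of all starters who have an event describes its safety. This stands, and the pooled table should stay.

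*Cycle of onset can be recovered.* All AEs are listed, onset dates are recorded (Section 7.4.5), chemistry and hematology are taken on Days 1, 15 and 29 of every cycle (Table 8), and laboratory changes from baseline are examined (Section 8.5.3). A reader might infer that the plan leaves no way to see accumulation; that would go too far. But a listing is not a pre-specified summary with an at-risk denominator, and laboratory changes do not cover clinical events. The DMC's judgement on whether five cycles is feasible draws on Part 1, which ends at two.

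*Rates by cycle have a bias of their own.* Patients dosed in Cycle 5 are those who did not progress or meet a toxicity rule in Section 4.3.2.1, so the rate per cycle can fall while toxicity accumulates. Dosing delays of up to 8 weeks (Section 5.3.1) and events reported during follow-up (Section 7.4.5) also blur attribution. This stands. It argues for a by-cycle table beside the pooled one, not in its place.

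*The 90% figure is not wrong.* A reader might infer that pooling makes the detection probability in Section 8.1 fail. The documents do not support that. The statement is conditional on exposed patients, is correct for 24, and is nowhere claimed for later cycles. A single Cycle 5 event appears in a pooled table as surely as in a by-cycle one, and a by-cycle table would not raise the probability. It is lower for an AE specific to a later cycle only if fewer than 22 patients reach that cycle.

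**Conclusion.** The gap is in the pre-specified summaries. The primary objective concerns repeated dosing, and no planned TEAE table separates one cycle from another or uses the patients dosed in a cycle as denominator. That the table cannot separate late from first-dose toxicity follows from the text alone. The amount of dilution rests on an assumption about retention: none if all 24 patients reach the cycle, half at 12, two thirds at 8. Early stopping is likely given the discontinuation rules and the 20 weeks to the Cycle 5 dose, but the documents give no rate.

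Section 8.1 contains no error. A sentence on how its figure carries over to later cycles would help the reader but is optional. The by-cycle summary should be added before the Part 2 analysis. It does not call the design or the pooled table into question.

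**What to change.** Keep the pooled table and add to Section 8.5.2, in substance:

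> For Part 2, TEAEs will also be summarised by cycle of onset, as the number and percentage of patients with an event and the worst CTCAE grade. The denominator is the number of patients who received that cycle's dose, shown in each column head. An event belongs to the cycle of the most recent dose before onset. Events reported during follow-up are attributed to the last cycle received or shown in a separate column. Patients on a reduced dose are flagged.

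Choose between the two options for follow-up events before the data are seen. Add a note that patients in later cycles are selected by the discontinuation rules, so a falling rate by cycle does not rule out cumulative toxicity.

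Optionally, say in Section 8.1 that the detection probability applies to AEs among all 24 dosed patients and that, for an AE specific to a later cycle, it depends on the number reaching that cycle. Give values for an assumed range, such as those in the table above.

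The cost is some wording and one more table from onset dates and dosing records already collected, with no extra patients or visits. The drawback is small, selected denominators in later cycles, where percentages will be unstable and should be read with the counts.
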